5.1 INCLUSION CRITERIA

Participants are eligible to be included in the study only if all of the following criteria apply:

Age

I 01. Participants must be 18 to 80 years of age, at the time of signing the informed consent.

Type of participant and disease characteristics

Patients with a clinical diagnosis of PN, as defined by all of the following:

I 02. Diagnosed by a dermatologist for at least 3 months before the Screening visit.

I 03. On the WI-NRS ranging from 0 to 10, patients must have an average worst itch score of ≥ 7 in the 7 days prior to Day 1.

NOTE: Baseline pruritus NRS average score for maximum itch intensity will be determined based on the average of daily NRS scores for maximum intensity (the daily score ranges from 0 to 10) during the 7 days immediately preceding randomization. A minimum of 4 daily scores out of the 7 days is required to calculate the baseline average score. For patients who do not have at least 4 daily scores reported during the 7 days immediately preceding the planned randomization date, randomization should be postponed until this requirement is met, but without exceeding the 28-day maximum duration of the screening period.

I 04. Patients must have a minimum of 20 PN lesions in total on both legs, and/or both arms and/or trunk, at Screening visit and on Day 1.

NOTE: Patients need to have bilaterally symmetrical lesions on the extremities. The presence of lesions on at least 2 body surface areas is required.

I 05. History of failing a 2-week course of medium-to-superpotent TCS or when TCS are not medically advisable.

NOTE: Failure is defined as patients who are unable to achieve and/or maintain remission and low disease activity (similar to IGA PN-S score of ≤ 2 [≤ 19 nodules]) despite treatment with a daily regimen of medium-to-superpotent TCS (\pm TCI as appropriate), applied for at least 14 days, or for the maximum duration recommended by the product prescribing information, whichever is shorter.

I 06. Have applied a stable dose of topical emollient (moisturizer) once or twice daily for at least 5 out of the 7 consecutive days immediately before Day 1 (NOTE: See exclusion criterion [E 20](#) for limitations regarding emollients; see background treatment with topical emollient in [Section 6.1.1](#)).

I 07. Participants must be willing and able to complete a daily symptom eDiary for the duration of the study.

Sex

I 08. Male or Female

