1.2.1 Estimands

The primary estimands defined for main endpoints are summarized in below [Table 3](#). More details are provided in [Section 4](#).

Table 3 - Summary of primary estimand for main endpoints

Endpoint Category	Estimands			
	Endpoint(s) ^a	Population	Intercurrent event(s) strategy and missing data handling	Population-level summary
Primary objective: To demonstrate the efficacy of dupilumab on itch response in participants with PN, inadequately controlled on topical prescription therapies or when those therapies are not advisable.				
Primary endpoint	Proportion of participants with improvement (reduction) in worst-itch numeric rating scale (WI NRS) by ≥ 4 from baseline to Week 24	ITT	
The intercurrent events will be handled as follows:
 
 Discontinuation of study treatment before Week 24: Off-study treatment data up to Week 24 will be included in the analysis (treatment policy strategy). Taking the prohibited medications/procedures and/or rescue medications^b prior to Week 24: Participants will be considered as non-responders (composite strategy). 
In addition, the missing data imputation rules are as follows:
 
 Having missing data at Week 24: Participants will be considered as non-responders 	CMH test adjusted by documented history of atopy (atopic or non-atopic), stable use of TCS/TCI (yes or no), region (countries combined), and baseline antidepressant use (yes or no).
Secondary objective: To demonstrate the efficacy of dupilumab on additional itch endpoints in participants with PN, inadequately controlled on topical prescription therapies or when those therapies are not advisable.				

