Secondary endpoint	Change from baseline in WI-NRS at Week 24	• ITT	
The intercurrent events will be handled as follows:
 
 Discontinuing the study treatment: all data collected following schedule after treatment discontinuation will be used in the analysis (treatment policy strategy). Taking the prohibited medications/procedures and/or rescue medications^b prior to Week 24: data will be set to missing values after the medication usage, and the participant's worst postbaseline value on or before the time of the medication usage will be used to impute missing endpoint value (for participants whose postbaseline values are all missing, the participant's baseline will be used to impute the missing endpoint value) (hypothetical strategy) 
In addition, the missing data imputation rules are as follows:
 
 After discontinuation of the study treatment due to lack of efficacy prior to Week 24: WOCF approach will be used to impute missing data if needed². After discontinuation of the study treatment due to reasons other than lack of efficacy prior to Week 24: multiple imputation (MI) approach will be used to impute missing endpoint value, and this multiple imputation will use all participants excluding participants who have taken the prohibited medications and/or rescue medications prior to Week 24 and excluding participants who discontinue due to lack of efficacy prior to Week 24. 	ANCOVA model with intervention group, documented history of atopy (atopic or non-atopic), stable use of TCS/TCI (yes or no), region (countries combined), baseline antidepressant use (yes or no), and relevant baseline measurement as covariates is used. Statistical inference obtained from all imputed data by ANCOVA model will be combined using Rubin's rule.

a Additional secondary objectives/endpoints are not included in this table but would be handled with a similar strategy as the endpoint type (ie continuous, proportion, time-to-event) at other weeks

b Prohibited medications and/or rescue medications are listed in [Table 5](#).

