4 STATISTICAL ANALYSES

4.1 GENERAL CONSIDERATIONS

In general, continuous data will be summarized using the number of observations available, mean, standard deviation (SD), median, minimum, and maximum. Categorical and ordinal data will be summarized using the count and percentage of participants.

The baseline value of efficacy parameters is defined as the last available value before randomization and prior to the first dose of study medication unless below eDiary data (WI-NRS, skin Pain-NRS and Sleep-NRS) score or otherwise specified.

The baseline for weekly average WI-NRS (skin Pain-NRS and Sleep-NRS) score is defined as the average of daily non-missing scores obtained during the 7 days prior to randomization.

The baseline value of the other parameters is defined as the last available value prior to the first dose of investigational medicinal product (IMP) if the participant is treated, or the last available value up to randomization if the participant is not exposed to IMP.

Observation period

The observation period will be divided into 4 segments:

- The **pre-treatment period** is defined as the period up to first IMP administration.
- The **treatment-emergent (TE) period** is defined as the period from the first IMP administration to the last IMP administration + 98 days. The treatment-emergent period includes the following 2 periods:
 - The **on-treatment period** is defined as the period from the first IMP administration to the last administration of the IMP + 14 days
 - The **residual treatment period** is defined as the period from the end of the on-treatment period to the end of the treatment-emergent period.
- The **post-treatment period** is defined as the period from the end of the treatment-emergent period.

The on-study observation period is defined as the time from start of intervention until the end of the study defined as the status date collected on e-CRF page “Completion of End of Study”.

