4.3 PRIMARY ENDPOINT(S) ANALYSIS

4.3.1 Definition of endpoint(s)

The primary endpoint for this study is the proportion of participants with improvement (reduction) in worst-itch numeric rating scale (WI-NRS) by ≥ 4 from baseline to Week 24.

WI-NRS is a patient-reported outcome (PRO) comprised of a single item rated on a scale from 0 (“No itch”) to 10 (“Worst imaginable itch”). Participants are asked to rate the intensity of their worst pruritus (itch) over the past 24 hours using this scale.

The weekly average WI-NRS score at each week, which is defined as the average of daily non-missing scores within the week window of each week (see [Section 5.4](#)), will be used for analyses.

For efficacy analysis, [Table 5](#) presents the prohibited and rescue medications/procedures which will be considered as intercurrent events if the last column indicates as “Yes” and therefore be handled in the estimands for endpoints defined in [Table 3](#).

Table 5 - Prohibited medications/procedures and rescue medications that impact efficacy

Medication/procedure	Comment	Data to be set as non-responder after taking medication in the main statistical analysis (Yes/No) ^a /Selection criteria
Prohibited medications/procedures		
Systemic immunosuppressive/immunomodulating drugs (eg, systemic corticosteroids, cyclosporine, mycophenolate-mofetil, interferon gamma, Janus kinase inhibitors, azathioprine, methotrexate, hydroxychloroquine, dapsone, sulfasalazine, colchicine, etc)	IMP to be discontinued	Yes (CDG ^b Immunosuppressant drugs Narrow and SDG ^b Corticosteroids Narrow)
Other monoclonal antibodies (that are biological response modifiers).	IMP to be discontinued	Yes (SDG ^b SDGMonoclonal antibodies Narrow)
Phototherapy, including tanning beds.	IMP to be discontinued	Yes (CMQ ^b HLT Phototherapies, CMQ ^b Tanning_single PT)
Naltrexone or other opioid antagonist	IMP to be discontinued	Yes (SDG ^b Analgesia producing opioids NARROW)
Gabapentin, pregabalin, and thalidomide	IMP to be discontinued	Yes (CDG ^b Gabapentin mono and multi ingredients, Pregabalin mono and multi ingredients, or Thalidomide mono and multi ingredients)
Paroxetine, fluvoxamine or other SSRIs.	No IMP discontinuation, see requirement in the footnote	Yes ^{c,d} (CDG ^b N06AB selective serotonin reuptake inhibitors)
SNRIs.	No IMP discontinuation, see requirement in the footnote	Yes ^{c,d} (CDG ^b serotonin and norepinephrine reuptake inhibitors)

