4.3.2 Main analytical approach

The primary estimand for the primary endpoint is the treatment policy/composite approach as defined in [Table 3](#).

The primary analysis population for the efficacy endpoints will be the ITT population.

The following null hypothesis H0 and alternative hypothesis H1 will be tested for dupilumab against placebo:

- H0: No treatment difference between dupilumab and placebo.
- H1: There is a treatment difference between dupilumab and placebo

The primary analysis will be conducted by using Cochran–Mantel–Haenszel test (CMH) test adjusted by documented history of atopy (atopic or non-atopic), stable use of TCS/TCI (yes or no), region, and baseline anti-depressant use (yes or no). Comparisons of the response rates between dupilumab and placebo will be derived. In addition, odds ratio and response rate difference as well as the corresponding 95% confidence intervals (CI) will be provided along with the p-values.

As defined in [Table 3](#) for participants discontinuing the study treatment before Week 24, their off-study treatment values measured up to Week 24 will be included in the analysis. Participants taking the prohibited medications/procedures and/or rescue medications (see [Table 5](#)) prior to Week 24 or having missing data at Week 24 will be considered non-responders.

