The DLQI is a PRO developed to measure dermatology-specific HRQoL in adult participants. The instrument comprises 10 items assessing the impact of skin disease on participants' HRQoL over the previous week. The items cover symptoms, leisure activities, work/school or holiday time, personal relationships including intimate, the side effects of treatment, and emotional reactions to having a skin disease. It is a validated questionnaire used in clinical practice and clinical trials. Response scale is a 4-point Likert scale (0 = "not at all" and 3 = "very much") for nine items. The remaining one item about work/studying asks whether work/study has been prevented and then (if "No") to what degree the skin condition has been a problem at work/study; the item is rated on a 3-point Likert scale ("Not at all" to "A lot"). Overall scoring ranges from 0 to 30, with a high score indicative of a poor HRQoL.

Time-to-event secondary efficacy endpoint

Time to first onset of effect on pruritus defined as an improvement (reduction) in WI-NRS by ≥ 4 from baseline during the 24-week treatment period will be analyzed using the Cox proportional hazards model, including treatment, documented history of atopy (atopic or non-atopic), stable use of TCS/TCI (yes or no), region, and baseline anti-depressant use (yes or no). The hazards ratio, its 95% confidence interval and p-value will be reported. Kaplan-Meier curves will be also provided.

For time to first WI-NRS response (WI-NRS by ≥ 4 from baseline), participants who receive the prohibited medications and/or rescue medications (see [Table 5](#)), data prior to start of the medications will be used, but after medication start, the participants' data will not be used and they will be censored at Week 24 (ie, Day 172). For other participants, all available data up to Week 24 (ie, Day 172) including those collected during the off-treatment period will be used. Participants without events will be censored at Day 172 or their last WI-NRS assessment date if discontinued from the study, whichever is earlier.

Secondary efficacy endpoints that measure binary responses

Secondary efficacy endpoints that measure binary responses will be analyzed in the same fashion as the primary endpoint using primary statistical model.

Continuous secondary efficacy endpoints

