The primary estimand for continuous secondary efficacy endpoints is defined in [Table 3](#) and will be analyzed using an analysis of covariance (ANCOVA) model with intervention group, documented history of atopy (atopic or non-atopic), stable use of TCS/TCI (yes or no), region (countries combined), baseline antidepressant use (yes or no), and relevant baseline measurement as covariate, with intercurrent event strategy and missing data handling as defined as in [Table 3](#). Specifically, data of participants taking the prohibited medications/procedures and/or rescue medications will be set to missing after the medication usage, and the worst postbaseline value on or before the time of the medication usage will be used to impute missing endpoint value (for participants whose postbaseline values are all missing, the baseline will be used to impute). Participants who discontinue the treatment prematurely are encouraged to follow the planned clinical visits and in those participants who did not take the prohibited medications/procedures

and/or rescue medications, all data collected after treatment discontinuation will be used in the analysis. For these participants, missing data may still happen despite all efforts have been tried to collect the data after treatment discontinuation. For participants who discontinue due to lack of efficacy, all data collected after discontinuation will be used in the analysis, and a WOCF approach will be used to impute missing data if needed. For participants who discontinued not due to lack of efficacy, a multiple imputation (MI) approach will be used to impute missing endpoint value, and this MI method will use all participants excluding participants who have taken the prohibited medications/procedures and/or rescue medications prior to timepoint of endpoint of interest and excluding participants who discontinue due to lack of efficacy.

Each of the imputed complete data will be analyzed by fitting an ANCOVA model as described above. The imputation number will be about 40. Statistical inference obtained from all imputed data will be combined using Rubin's rule. Descriptive statistics including number of participants, mean, standard error, and least squares (LS) mean changes (and standard error) will be provided. In addition, difference of the dupilumab group against placebo in LS means and the corresponding 95% confidence intervals (CI) will be provided along with the p-values.

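### Baseline WI-NRS is left out of the WI-NRS responder analysis and the matching Cox model without a stated reason; adjusting for it may give a small gain in precision

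*SAP*

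**What the plan says.** The primary endpoint (SAP 4.3.1) is the proportion of participants with "improvement (reduction) in worst-itch numeric rating scale (WI-NRS) by ≥ 4 from baseline to Week 24". SAP 4.3.2 tests it with a CMH analysis "adjusted by documented history of atopy (atopic or non-atopic), stable use of TCS/TCI (yes or no), region, and baseline anti-depressant use (yes or no"). Table 3 in SAP 1.2.1 repeats this as a "CMH test adjusted by documented history of atopy (atopic or non-atopic), stable use of TCS/TCI (yes or no), region (countries combined), and baseline antidepressant use". For time to the same response, SAP 4.4.2 specifies a Cox model "including treatment, documented history of atopy (atopic or non-atopic), stable use of TCS/TCI (yes or no), region, and baseline anti-depressant use (yes or no"). Baseline WI-NRS is in neither list.

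It is included where the same scale is analysed as a continuous variable. For change in WI-NRS, Table 3 gives an ANCOVA with "baseline antidepressant use (yes or no), and relevant baseline measurement as covariates is used". SAP 4.4.2 says the same ("baseline antidepressant use (yes or no), and relevant baseline measurement as covariate"), and the sample code in SAP 5.5 carries baseline WI-NRS in both the imputation and the analysis model.

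The variable is available for everyone. SAP 4.1 says that the baseline weekly score "is defined as the average of daily non-missing scores obtained during the 7 days prior to randomization". Under Protocol 5.1 (I 03), "patients must have an average worst itch score of ≥ 7 in the 7 days prior to Day 1", with at least four of the seven daily scores present.

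Randomisation (Protocol 6.3) is stratified by atopy, TCS/TCI use and country, not by baseline itch. Antidepressant use is in the adjustment set although it is not a stratification factor. Neither document explains why baseline WI-NRS is treated differently.

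**The concern.** Baseline WI-NRS is half of the outcome's arithmetic. A participant who enters at 7 must reach 3 or less to respond; one who enters at 10 must reach 6 or less. A baseline variable that predicts the outcome reduces the standard error when it is adjusted for, and the plan does this for every continuous itch endpoint. It does not do so for the endpoint that decides whether the study is positive, or for time to that response. What could be lost is some precision in the primary comparison and in the Cox analysis. Validity is not in question.

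**Working it through.** **1. The plan's own figure.** SAP section 2 gives 56 evaluable per arm for 90% power (Fisher exact, two-sided 0.05), 15% dropout and 75 randomised per arm. The response rates are redacted, so 56 cannot be reproduced forward. Working backward by exact enumeration, pairs that give 90% power at 56 per arm include 5% v 28.2%, 15% v 43.7% and 30% v 62.0%, differences of about 23 to 32 points. Every power figure below therefore uses assumed rates.

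**2. How much baseline WI-NRS could explain.** The documents give no correlation between baseline and response. Assume that baseline lies on 7 to 10 (I 03), that Week 24 itch depends linearly on it with residual SD 2.0 to 3.0, that response is 15% and 45%, and that 10% are set to non-response. The average within-arm R² is then:

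| Slope of Week 24 on baseline | R² |
|---|---|
| 1 | 0 |
| 0.75 | 0.002–0.004 |
| 0.5 | 0.007–0.016 |
| 0.25 | 0.015–0.033 |
| 0 | 0.027–0.057 |

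The more closely Week 24 itch tracks baseline, the less baseline predicts a 4-point fall, because the target score moves with it.

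**3. What that is worth.** Variance is multiplied by (1 − R²). At the top value, the SE is multiplied by √(1 − 0.057) = 0.971, and 75 per arm acts like 75 / 0.943 = 79.5. For 15% v 43.7% (normal approximation), moving R² from 0 to 0.02 to 0.05 takes power from 92.7% to 93.1% to 93.8% at 56 per arm, and from 97.7% to 98.0% to 98.3% at 75 per arm.

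Starting from the plan's nominal 90%, power = Φ((1.96 + 1.2816)/√(1 − ρ²) − 1.96). This gives 90.3% at ρ = 0.1, 91.1% at 0.2, 91.4% at 0.22 and 96.3% at 0.5. A 5-point gain needs ρ of about 0.45, or R² = 0.45² = 0.20, more than three times the top value in step 2.

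**4. The form of the test.** SAP 5.3 lists four regions. If the four factors are fully crossed there are 2 × 2 × 4 × 2 = 32 cells, or 150 / 32 = 4.7 participants per cell on average. Four sets of simulated trials with 150 participants compare that CMH with a main-effects model that includes linear baseline WI-NRS:

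| Assumed response | CMH, 32 cells | Main effects + baseline | Total gain (points) | Baseline alone (points) |
|---|---|---|---|---|
| about 18% v 41% | 83.6–85.7% | 87.5–88.5% | 2.8–3.9 | 0.1–0.7 |
| 15% v 40% | 88.5–89.6% | 93.0–94.4% | 4.1–5.1 | −0.3 to +0.9 |
| difference 21–22 points | 82.3–85.0% | 88.4–88.9% | 3.9–5.6 | −0.6 to +1.6 |
| about 18% v 40% | 80–85% | 84–85% | about 1–3 | −0.6 to +1.4 |

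Ranges run over the assumed slope of Week 24 on baseline. Rows 1 and 2 use a linear risk-difference model with robust SE; row 3 uses a logistic model with a standardised risk difference. Rows 1 and 2 rest on 4,000 trials per setting and row 3 on 3,000, so one power figure carries a Monte Carlo SE of about 0.5 point. Rows 1 and 2 assume atopy 50%, TCS/TCI use 60%, and antidepressant use 8% and 15% respectively. Row 2 gives the stratification factors no prognostic value, which favours the model over crossed cells.

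In row 1, replacing crossed cells by main effects accounts for 3.2 of 3.9, 3.1 of 3.7 and 2.7 of 2.8 points, that is 82% to 96% of the gain.

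**5. Baseline as another stratum.** Under row 2's assumptions, splitting baseline at 8.5 gives 64 cells. Power falls to 82.9–84.9%, and the information relative to an unstratified comparison falls from 0.83 to 0.71.

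**6. Test size.** The CMH rejected 4.5% to 5.1% of null trials. The models with a plain robust SE rejected up to about 6%, so part of the larger gains may reflect a slightly liberal test.

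**The case against.** The strongest reply is that this is a choice between two valid methods. The CMH holds its size. Chance imbalance in baseline itch is ordinary sampling variation that the test already allows for. The endpoint is change from each participant's own baseline, which removes part of the association. Baseline WI-NRS is summarised by arm (SAP 5.3). A baseline-adjusted itch result is already inside the alpha-controlled hierarchy, because percent change in WI-NRS at Week 24 (SAP 4.6) comes from the ANCOVA. All of this stands.

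A logistic model also has a cost. At 18% v 41% there are about 75 × 0.18 + 75 × 0.41 = 44 responders for eight coefficients (treatment, atopy, TCS/TCI, three for region, antidepressant use, baseline). The CMH also underlies the hybrid and tipping-point analyses and the key secondary endpoints. These are fair reasons not to insist on replacing the primary test.

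They do not explain the Cox model. It is already a main-effects model, so one more covariate raises no problem of sparse cells.

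A reader might also infer three stronger things that the documents do not support:

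- **That the primary comparison is biased or its type I error inflated.** Nothing in the plan or in the simulations shows this.
- **That substantial power is lost.** That needs ρ near 0.45 to 0.5, a value found nowhere in the documents and hard to reach when entry restricts baseline to three points of the scale.
- **That the SAP specifies 32 strata.** It says only that the test is adjusted. Protocol 9.4.1 describes stratification factors plus a covariate, and no CMH code is supplied. Full crossing is the usual reading but is not stated.

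**Conclusion.** The omission is real and unexplained, and it is inconsistent with the continuous WI-NRS models. Its consequence is small. Baseline WI-NRS alone is likely to add about 0 to 1 point of power, and nothing if Week 24 itch tracks baseline one for one. If the CMH is fully crossed, a main-effects model with baseline WI-NRS gains roughly 1 to 5 points in total (one setting reached 5.6), mostly from avoiding sparse cells. These sizes depend on assumed response rates, factor prevalences and a linear relation between Week 24 and baseline itch. No size was calculated for the Cox model. This is a low-cost improvement; the planned primary analysis can stand without it.

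**What to change.** Before database lock and unblinding:

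- **SAP 4.4.2:** add baseline WI-NRS as a linear covariate to the Cox model.
- **SAP 4.3.4:** add a supplementary logistic analysis of the WI-NRS responder endpoints, with the same responder definition and intercurrent-event handling as the main analysis. Terms: treatment; main effects for atopy, TCS/TCI use, region and antidepressant use; linear baseline WI-NRS. Report a standardised risk difference with a robust 95% CI that carries a small-sample correction.
- **Fallback:** state in advance what happens if the fit fails or separates, for example Firth's penalised likelihood.
- **SAP 4.3.2:** state whether the CMH fully crosses its four factors and why baseline WI-NRS is omitted. Do not add baseline as a further CMH stratum, which would lower power.

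Making the logistic model the primary test, with the CMH as supportive, is optional. It would also require a decision on the analyses that now rest on the CMH.

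The cost is SAP wording and a few lines of code, with no new data. The downside is small: a model-based estimate, and odds and hazard ratios that become conditional on baseline itch.
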